Blood specimens for selected biomarkers will be collected at Screening, Baseline and at Weeks: 2, 4, 8, 12, 16, 20, 24, 30, 36, 42, 48, 50, 52, 56, 60, 64, 72, every 12 weeks thereafter, 30 Day Follow-up and ESDD (if applicable). The timepoints may differ depending on the specific biomarker and will be outlined in the Central Lab manual.

PK blood draws will be collected at Weeks 2, 4, 8, 12, 16, 20, 24, 30, 36, 42 and 48 and Week 60 and every 12 weeks in the OLE.

Smoking status will be collected at Weeks 4, 8, 12, 16, 20, 24, 30, 36, 42, 48, 52, 56, 60, 64, 72 and every 12 weeks thereafter.

Women determined to be of child bearing potential will have a urine test as listed in [Table 6-1](#) and every 4 weeks during the OLE starting with Week 64.

Complete physical exam will be performed at Weeks 12, 24 and 48, symptom directed physical exam will be completed as needed at all other visits.

NCAA Form A with spirometry should be completed by the Investigator or Sub-Investigator at all study visits (except Week 2) and during the OLE at Weeks 56, 60, 64, 72 and every 12 weeks thereafter. The NCAA Form A should also be performed at the time of initiation of second-line therapy. Situations where subjects have comorbid or irreversible conditions that may interfere with response assessment, the check box on the NCAA indicating that the abnormality is entirely explained by a non-GVHD documented cause should be marked. Organ-specific response measures may be delayed until the following visit to allow for resolution of a non-GVHD issue. All other organs should still be scored. A 2 min or 6 min walk test should be performed at Baseline/Day 1, Weeks 24 and 48/ESDD, when medically feasible. Trained study personnel may complete spirometry and walk test portion of NCAA Form A.

LSS and NCAA Form B should be completed by the subject. The Subject is to read the questionnaire by himself/herself and write/mark answers directly on the questionnaire. The PROs will be completed at all study visits (except Week 2) and during the OLE will be assessed at Weeks 56, 60, 64, 72 and every 12 weeks thereafter. One question has been added to the LSS which asks which two domains are most impactful to the subject.

Document study drug dispensation and accountability for all study drugs dispensed. No study drug will be dispensed at Weeks 2, 30, 42 and 50, drug accountability must be done at dispensing visits.

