6. EFFICACY ANALYSES

6.1. Definition of the Primary Efficacy Endpoint

The primary endpoint is BORR by 24 weeks, defined as the proportion of subjects who achieve a complete or partial overall response (CR or PR) as assessed by the NCAA (Appendix 3) within 24 weeks, in the setting of add-on therapy to systemic corticosteroids as part of first-line therapy for cGVHD.

At each assessment time point, organ-specific responses will be determined according to Appendix 2. An overall time point response across all involved organs will then be determined according to Table 3. The best overall response across all time points up to 24 weeks will be used to calculate BORR by 24 weeks.

Table 3. Criteria for time point response determination

Response Category	Response Criteria
Complete response (CR)	Resolution of all cGVHD manifestations in each organ or site as described in the NCAA organ response determination table
Partial response (PR)	Improvement of at least 1 organ or site, without progression in any other organ or site as described in the NCAA organ response determination table.
Stable disease (SD)	Neither sufficient improvement to qualify for a PR nor sufficient decline to qualify for a PD
Progressive disease (PD)* * A flare is defined as acute worsening of signs and symptoms in any organ or site that occurs at least 4 weeks after PR/CR is achieved, which lasts ≤ 4 weeks.	
 • Worsening of signs and symptoms in any organ or site as described in the NCAA organ response determination table, taking the baseline as reference. OR • Increase in systemic corticosteroid dose to ≥ baseline dose (1 mg/kg/day) OR • Initiation of systemic immunosuppressive therapy other than systemic corticosteroids

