6.3. Analysis of the Primary Efficacy Endpoint

The primary analysis for BORR will be performed in the ITT Analysis Set, which includes all subjects who were randomized. Response rate will be summarized by count and percent of subjects with each ordinal response (CR, PR, CR or PR, SD and PD). A stratified Cochran-Mantel-Haenszel (CMH) Chi-square test will be performed to compare BORR (CR + PR) between ENTO and placebo-to-match (PTM) by 24 weeks. The difference in response rates between treatment groups and the corresponding 95% CIs will be presented.

If the entire NIH questionnaire is missing, then the organ and subject level statuses are missing. Missing individual NIH domain scores, for example, skin score, will lead to missing status for skin domain. In such a case, the subject level status will be based on the remaining available domain statuses. This is equivalent to imputing the missing domain status as ND or NA.

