Lower GI	NIH Lower GI Score 0 after previous involvement	Decrease in NIH Lower GI Score by 1 or more points	Increase in NIH Lower GI Score by 1 or more points, except from 0 to 1
Liver	Normal ALT, alkaline phosphatase, and Total bilirubin after previous elevation of 1 or more	Decrease by 50%	Increase by 2 × ULN
Lungs	- Normal %FEV1 after previous involvement - If PFTs not available, NIH Lung Symptom Score 0 after previous involvement	- Increase by 10% predicted absolute value of %FEV1 - If PFTs not available, decrease in NIH Lung Symptom Score by 1 or more points	- Decrease by 10% predicted absolute value of %FEV1 - If PFTs not available, increase in NIH Lung Symptom Score by 1 or more points, except 0 to 1
Joints and fascia	Both NIH Joint and Fascia Score 0 and P-ROM score 25 after previous involvement by at least 1 measure	Decrease in NIH Joint and Fascia Score by 1 or more points or increase in P-ROM score by 1 point for any site	Increase in NIH Joint and Fascia Score by 1 or more points or decrease in P-ROM score by 1 point for any site
Global	Clinician overall severity score 0	Clinician overall severity score decreases by 2 or more points on a 0-10 scale	Clinician overall severity score increases by 2 or more points on a 0-10 scale

ULN indicates upper limit of normal.

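### SAP 6.3 ignores an unscored organ even when it was last scored as progressed, so one incomplete visit can make a progressing subject a BORR responder

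*SAP*

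**What the plan says.** SAP 6.3 gives an unscored organ a missing status. It then states: "In such a case, the subject level status will be based on the remaining available domain statuses", and adds: "This is equivalent to imputing the missing domain status as ND or NA". The organ's previous status plays no part.

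SAP 6.1, Table 3, defines partial response as "Improvement of at least 1 organ or site, without progression in any other organ or site". Complete response needs resolution in every organ or site. Across visits, "The best overall response across all time points up to 24 weeks will be used to calculate BORR by 24 weeks". No confirmation is required, and progression at one visit does not block a response at another.

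NCAA visits to week 24 fall at weeks 4, 8, 12, 16, 20 and 24. Protocol 6.4 lets an organ measure be put off to the next visit while a non-GVHD problem resolves, and says of the rest: "All other organs should still be scored". SAP 6.3 reports CR and PR separately as well as combined, with the difference in response rates and its 95% CI. SAP 6.4.2 analyses duration of response (DOR) in responders only.

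**The concern.** Dropping a progressed organ from the visit assessment has the same effect as assuming that it no longer shows progression. That conflicts with the condition in Table 3 that no other organ has progressed. Because BORR keeps the best visit, one such gap is enough and later complete visits showing PD do not undo it. A CR is likewise possible while an organ involved at baseline is unscored. If that organ was stable, BORR is unchanged but the CR and PR counts shift.

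SAP 3.5 drops formal comparisons after early termination. What is at stake is therefore descriptive: BORR in each arm, its difference and CI, the CR/PR split, and who enters the DOR analysis.

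**Working it through.** **The plan's own figure.** An exact calculation for Fisher's test with 40 per arm, 50% versus 80% and two-sided 0.05 gives 74.9% power (stated: 75%), and 80/(1 − 0.2) = 100. Both reproduce and neither is disputed. They supply the planning rates used below.

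**Does the rule do this?** Take a subject with skin progressed and mouth improved at all six visits:

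| Case | Visit statuses, weeks 4 to 24 | Best response |
|---|---|---|
| All organs scored | PD, PD, PD, PD, PD, PD | PD |
| Skin unscored at week 12, SAP 6.3 as written | PD, PD, PR, PD, PD, PD | PR (responder) |
| Same, last skin status retained | PD, PD, PD, PD, PD, PD | PD |

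Conditions: if no other organ has improved, the week 12 visit becomes SD and the subject stays a non-responder. PD from a steroid increase or new systemic immunosuppression does not depend on organ scores and still holds. If the Global row of SAP Appendix 2 counts as a site (the SAP does not say) and shows "Clinician overall severity score increases by 2 or more points on a 0-10 scale", the visit stays PD.

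**How large?** The inputs other than the planning rates are assumptions:
- q = 0.02 to 0.10, the chance that the progressed organ is unscored at a visit
- m = 0.25 to 0.50, the share of non-responders who are mixed (one organ better, one worse)
- k = number of visits spent in that state
- true rates 50% and 80%, 50 per arm

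Share of mixed subjects converted: f = 1 − (1 − q)^k. For k = 2, f = 0.0396 at q = 0.02 and 0.19 at q = 0.10.

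Equal missingness, k = 2:
- Placebo rises by 0.5·m·f: from 0.5 × 0.25 × 0.0396 = 0.5 points to 0.5 × 0.50 × 0.19 = 4.75 points.
- ENTO rises by 0.2·m·f: from 0.2 to 1.9 points.
- The difference falls by (0.5 − 0.2)·m·f, from 30 to between 29.70 and 27.15.
- Expected extra responders per 50: 0.25-2.4 on placebo and 0.1-0.95 on ENTO. Each one moves its arm by 1/50 = 2 points.

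Other values of k, equal missingness:
- k = 1: f = q, and the difference is 28.5-29.85.
- k = 5, same m: the fall is 0.3 × 0.25 × 0.096 = 0.7 points at the low end and 0.3 × 0.50 × 0.41 = 6.1 at the high end, giving 23.9-29.3.

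Unequal missingness, k = 2:
- ENTO 10%, placebo 2%: 30 + 0.95 − 0.495 = 30.5 (m = 0.25), and 30 + 1.9 − 0.99 = 30.9 (m = 0.50).
- ENTO 2%, placebo 10%: 30 + 0.198 − 2.375 = 27.8, and 30 + 0.396 − 4.75 = 25.6.

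Equal response (50% in both arms), k = 2:
- Equal missingness: both arms rise by the same 0.5-4.75 points and the difference stays at zero.
- 10% in one arm and 2% in the other: a spurious 2.375 − 0.495 = 1.9 points (m = 0.25) to 4.75 − 0.99 = 3.8 points (m = 0.50), favouring the arm with more missing scores.

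For scale, the 95% CI half-width at 80% versus 50% with 50 per arm is 1.96 × √(0.25/50 + 0.16/50) = 17.7 points.

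**The case against.** The strongest reply is that the path seldom opens. Protocol 6.4 asks that other organs be scored. SAP Appendix 2 falls back on the lung symptom score when PFTs are unavailable, and liver response rests on chemistry scheduled at every visit. Form A has a box for a range-of-motion (P-ROM) site that was not assessed, and Appendix 2 counts "decrease in P-ROM score by 1 point for any site" as progression. But a printed box is no evidence of missing data, and the joint domain also has its own NIH score. All of this stands, and it limits the frequency without closing the path.

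The dilution figures also need a true difference between the arms, whereas SAP 2.3 reports a stop for lack of efficacy. That stands too: with equal response and equal missingness the difference is unbiased. An unscored organ may also truly have recovered, so not every conversion is an error. The plan simply cannot tell the cases apart.

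Changing the derivation after the interim stop has its own cost, which is why both results should be shown.

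A reader might infer that the rule influenced the futility decision. The documents do not show this. The SAP revision log dates its missing-data entry for 6.3 to 24 APR 2018, in the revision made for study discontinuation. That entry mentions only an entirely missing questionnaire. Which organ-level derivation the interim counts used is not stated.

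A reader might also infer that visits after second-line therapy count as responses, because the synopsis allows PR only if no further systemic therapy is needed and the PR rows of Tables 8-1 and 3 omit this. The PD rows of both tables list new systemic immunosuppression, so the condition is largely covered. Only whether that PD persists at later visits is open.

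**Conclusion.** The concern holds as a defect in the visit-level rule: SAP 6.3 as printed can turn Table 3 progression into a response through absent data alone. It needs an improved organ scored at the same visit, no therapy-defined PD, and no worsening of the Global row if that row counts.

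Its size is unknown. Under the stated assumptions with two visits at risk, the bias in a 30-point difference is 0.3 to 2.85 points towards zero, which is modest against the 17.7-point half-width. It grows with the number of visits at risk. No direction can be claimed for this trial: equal response with equal missingness leaves the difference unbiased although both rates are inflated, and unequal missingness can push it either way. SAP 6.6, on changes to the efficacy analyses, is redacted, so a rule there cannot be excluded.

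**What to change.** In SAP 6.3, state that:
- a visit at which an organ last scored as progressed is unscored, including one delayed under protocol 6.4, is not evaluable for CR or PR until that organ is rescored;
- a visit at which an organ involved at baseline is unscored cannot be CR;
- only an organ whose abnormality is marked as entirely explained by a documented non-GVHD cause is exempt;
- PD shown by a scored organ or a therapy criterion stands.

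Report BORR under this rule and under the current one, with the number of subjects per arm whose status changes. Label the change as made after the interim, and state which derivation the interim used. Separately, reconcile the synopsis with Tables 8-1 and 3 on whether PD from new systemic therapy persists at later visits.

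The work is SAP text and derivation code on existing data. The downside is that a few incomplete visits stop counting, so both rates may be slightly lower. A true recovery counts at the next scored visit. It is lost only if the organ stays unscored at every remaining visit to week 24, with chance q^j for j visits left: 0.04-1% for two and 2-10% for one, at the assumed q. The rule does not catch an organ last scored as stable that first worsens at the unscored visit.

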6.4. Secondary Efficacy Endpoints

6.4.1. Definition of Secondary Efficacy Endpoints

The key secondary endpoints are:

- Change from baseline in the skin domain of the LSS at 24 weeks
- Change from baseline in the mouth domain of the LSS at 24 weeks
- Change from baseline in the eyes domain of the LSS at 24 weeks
- Change from baseline in the total score of the LSS at 24 Weeks

Other secondary endpoints include:

- Duration of response, defined as the time from the documentation of BORR to the documentation of PD as defined in [Table 3](#). Note that a flare does *not* constitute an end to response. A sensitivity analysis for DOR could consider a flare does constitute an end to response.
- Proportion of subjects who ever achieve at least 50% reduction in systemic corticosteroid dose relative to baseline, where % reduction is calculated as (systemic corticosteroid dose at 24 weeks – baseline systemic corticosteroid dose) / baseline systemic corticosteroid dose.
- Proportion of subjects who initiate second-line therapy for cGVHD, defined as receiving any therapy besides systemic corticosteroids or study drug for the treatment of cGVHD. Inhaled and topical steroids are not considered second-line therapy.
- Failure-free survival (FFS), defined as the time from randomization to the earliest of first documentation of systemic therapy change, non-relapse mortality, or recurrent malignancy

- Safety and tolerability of ENTO

6.4.2. Analysis Methods for Secondary Efficacy Endpoints

The key secondary endpoints will be analyzed using a two sample z-test at week 24.

Other secondary endpoints will be analyzed as follows:

DOR and FFS will be analyzed using the Kaplan-Meier (KM) method and stratified logrank test. Kaplan-Meier summary statistics (median, 95% CI for median, and 25th, 75th percentiles) and number and percentage of events will be presented by treatment group. A stratified Cox proportional hazards model will be used to estimate the hazard ratio and corresponding 95% CI. A KM survival plot will also be provided. Data for subjects who do not experience an event will be censored at the date of last visit. DOR will be analyzed only on subjects who responded.

Proportion of subjects with at least 50% reduction in systemic corticosteroid dose relative to baseline and proportion of subjects who initiated a second-line therapy for cGVHD will be analyzed similarly to the primary endpoint.

Line plot of change from baseline in each domain and total of LSS will be done.

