8.5.2. Secondary Analyses

A sequential testing strategy will be implemented to preserve the overall type I error rate across the primary and key secondary endpoints of the study at a 2-sided significance level of 0.05. The primary endpoint analysis will serve as the gatekeeper for the key secondary endpoint analyses, ie, the primary efficacy endpoint must be met before the key secondary efficacy endpoints can be tested. The key secondary endpoints included in this sequential testing approach are (1) change from baseline in the skin domain of the LSS at 24 weeks, (2) change from baseline in the mouth domain of the LSS at 24 weeks, (3) change from baseline in the eyes domain of LSS at 24 weeks, and (4) change from baseline in the total score of the LSS at 24 weeks.

If the primary hypothesis is rejected, the key secondary endpoints will be sequentially tested at the 2-sided 0.05 significance level in the order listed above. If a null hypothesis is not rejected, formal sequential testing will stop and only nominal significance will be cited for the remaining endpoints.

The key secondary endpoints will be analyzed using a MMRM model that includes all available data at baseline and all post-baseline visits. The model will include terms for baseline value, stratification factor, treatment, visit, and treatment-by-visit interaction. The Kenward-Roger approximation will be used to estimate the denominator degrees of freedom and adjust standard

errors. Treatment comparisons will be generated within the MMRM model based on the linear contrast of the least square means at all-time points. Adjusted means and 95% CIs will be presented by treatment group. Plots of mean (\pm SE) change from baseline over time will be provided by treatment group. Additional sensitivity analyses to further evaluate the impact of missing data may be performed and will be specified in the statistical analysis plan (SAP).

[figure not shown]
Other secondary endpoints will be analyzed as follows:

DOR and FFS will be analyzed using the Kaplan-Meier (KM) method and stratified logrank test. Kaplan-Meier summary statistics (median, 95% CI for median, and 25th, 75th percentiles) and number and percentage of events will be presented by treatment group. A stratified Cox proportional hazards model will be used to estimate the hazard ratio and corresponding 95% CI. A KM survival plot will also be provided. Data for subjects who do not experience an event will be censored at the date of last visit.

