3. GENERAL CONSIDERATIONS FOR DATA ANALYSES

Analysis results will be presented using descriptive statistics. For categorical variables, the number and percentage of subjects in each category will be presented; for continuous variables, the number of subjects (n), mean, standard deviation (SD) or standard error (SE), median, first quartile (Q1), third quartile (Q3), minimum, and maximum will be presented. Time-to-event endpoints will be summarized using median and quartiles of the Kaplan-Meier (KM) estimates.

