3.3. Strata and Covariates

Subjects will be randomly assigned to treatment groups via the interactive web response system (IWRS) in a 1:1 ratio using a stratified randomization schedule. Stratification will be based on the following factors:

- calcineurin inhibitor or mycophenolate mofetil (MMF) use (no vs. yes) at Screening
- moderate vs. severe cGVHD as determined by the NIH cGVHD Diagnosis and Staging Criteria (NCDSC) at the Screening

If there are discrepancies in stratification factor values between the IWRS and the clinical database, the baseline values recorded in the clinical database will be used for analyses. Both stratification factor values can be defined based on questionnaire data collected at the screening visit, and concomitant medicine data.

Efficacy endpoints will be evaluated using stratification factors as covariates or stratification variables for analyses.

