11. SAP REVISION

Revision Date (DD MMM YYYY)	Section	Summary of Revision	Reason for Revision
24 APR 2018	2.3	Week 14 Analysis deleted	Study discontinuation due to lack of efficacy
24 APR 2018	2.4	Week 48 Analysis deleted	Study discontinuation due to lack of efficacy
24 APR 2018	2.5	Section number changed to 2.3. Added description of final analysis.	Study discontinuation due to lack of efficacy
24 APR 2018	3.1.2	Deleted the definition of Safety Analysis Set for OLE phase	Study discontinuation due to lack of efficacy and very few OLE AE occurrences
24 APR 2018	3.1.3	Deleted the immunosuppressant PK Analysis Set	Study discontinuation due to lack of efficacy
24 APR 2018	3.4	Deleted the specified subgroup analysis	Study discontinuation due to lack of efficacy
24 APR 2018	3.5	Deleted the multiple hypothesis testing	Study discontinuation due to lack of efficacy
24 APR 2018	3.6.1	Deleted the MMRM analysis for LSS. Moved the language of Lab value missing from section 3.7	Study discontinuation due to lack of efficacy
24 APR 2018	3.8.2	Added “for All Except ECG” at the end of title of Table 1	To clarify the windows apply to all endpoints but ECG
24 APR 2018	3.8.2	Deleted Table 3	Study discontinuation due to lack of efficacy and very few OLE AE occurrences
24 APR 2018	3.8.2	Added “FU-30 Day” nominal visit	To summarize the data more precisely
24 APR 2018	4.1	Deleted “Number and percentage of randomized subjects in the PP Analysis Set” and “The reasons for exclusion from the PP Analysis Set will be summarized separately”	Study discontinuation due to lack of efficacy
24 APR 2018	4.2.2	Changed the formula of calculating adherence	The PPI usage is not recorded in the eCRF thus day based formula is used to calculate adherence
24 APR 2018	6.3	Added the missing imputation when the entire NIH questionnaire is missing	To clarify the missing imputation
24 APR 2018	6.4.2	Deleted the MMRM analysis	Study discontinuation due to lack of efficacy
24 APR 2018	6.5.1	Deleted two exploratory endpoints related to flares	Study discontinuation due to lack of efficacy and very few flares

24 APR 2018	6.5.2	Deleted the time to first flare analysis and methods handling multiple occurrences	Study discontinuation due to lack of efficacy and very few flares
24 APR 2018	6.6	Added all new changes to the section	Study discontinuation due to lack of efficacy
24 APR 2018	7.1.5.1	Clarify the definition of treatment emergent	To clarify the definition of treatment emergent

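### The week-24 z-test for the four key secondary LSS scores uses no strata, against SAP 3.3, and no baseline adjustment, against protocol 8.5.2; the likely cost is precision in descriptive results

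*SAP*

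**What the plan says.** Protocol 8.5.2 analyses the key secondary endpoints (change from baseline to week 24 in the LSS skin, mouth, eyes and total scores) with an MMRM over all post-baseline visits: "The model will include terms for baseline value, stratification factor, treatment, visit, and treatment-by-visit interaction". It adds: "Treatment comparisons will be generated within the MMRM model based on the linear contrast of the least square means". LSS is collected at baseline, at weeks 4, 8, 12, 16, 20 and 24, and again at weeks 30 to 48.

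The SAP replaces this. Section 6.4.2 reads: "The key secondary endpoints will be analyzed using a two sample z-test at week 24". The same section also plans a line plot of LSS change. The SAP 11 entry for Section 3.6.1 says "Deleted the MMRM analysis for LSS", a further entry records the deletion at 6.4.2, and both give study discontinuation for lack of efficacy as the reason. SAP 6.6, on changes from the protocol's efficacy analyses, is redacted.

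SAP 3.3 sets a general rule: "Efficacy endpoints will be evaluated using stratification factors as covariates or stratification variables for analyses". SAP 3.5 says that, because of early termination, no formal comparisons will be made.

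**The concern.** A two-sample z-test on week-24 change has no place for strata, so SAP 6.4.2 and SAP 3.3 cannot both be followed. The test subtracts baseline but does not adjust for it as a covariate, and it uses no other visit. For BORR, SAP 6.3 names an effect estimate: "The difference in response rates between treatment groups and the corresponding 95% CIs will be presented". For LSS, the readable SAP names arm summaries (SAP 3), a test and a plot, but no between-arm difference with an interval.

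At stake are how precise the LSS treatment differences are, given data already collected, and whether the reported standard errors match the stratified design.

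**Working it through.** **1. The plan's own figure.** The documents give no power, SD or effect size for LSS. The only sample-size statement concerns BORR: 50% vs 80%, 40 per arm, Fisher's exact test, two-sided 0.05, 75% power. Exact enumeration gives 74.9%, and 40/(1 − 0.20) = 50 per arm. Both reproduce, and this point does not affect them.

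**2. The SAP against itself.**

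| Endpoint | Readable SAP analysis | Strata used? |
|---|---|---|
| BORR | stratified CMH (6.3) | yes |
| DOR, FFS | "DOR and FFS will be analyzed using the Kaplan-Meier (KM) method and stratified logrank test", plus stratified Cox (6.4.2) | yes |
| Steroid reduction; second-line therapy | as for the primary (6.4.2) | yes |
| Four LSS scores | two-sample z-test (6.4.2) | none named |

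The 24 April 2018 revisions list Sections 3.4, 3.5, 3.6.1 and 6.4.2, but not 3.3. LSS is therefore the exception, and termination was not treated as a general reason to drop strata.

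**3. Baseline adjustment.** Assumptions: complete data, equal variances at baseline and week 24, correlation r = 0.3, 0.5 or 0.7, strata explaining nothing.
- Variance ratio, change score over ANCOVA: 2(1 − r)/(1 − r²) = 2/(1 + r). Chance baseline imbalance is already inside this ratio.
- ANCOVA pays for three covariates (baseline and two strata) by the factor 1 + 3/(N − 6): 1.032 at N = 100 and 1.068 at N = 50.
- Critical values: 1.96 for the z-test; t on N − 5 df for ANCOVA, 1.985 at N = 100 and 2.014 at N = 50.
- Width ratio = √(net variance ratio) × 1.96/t.

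| r | 2/(1 + r) | Net ratio, N = 100 | Width ratio | Net ratio, N = 50 | Width ratio |
|---|---|---|---|---|---|
| 0.3 | 1.538 | 1.491 | 1.221 × 0.987 = 1.21 | 1.440 | 1.200 × 0.973 = 1.17 |
| 0.5 | 1.333 | 1.292 | 1.137 × 0.987 = 1.12 | 1.248 | 1.117 × 0.973 = 1.09 |
| 0.7 | 1.176 | 1.140 | 1.068 × 0.987 = 1.05 | 1.101 | 1.049 × 0.973 = 1.02 |

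N = 100 is the planned size; N = 50 is assumed.

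**4. Unequal variances.** With c = week-24 SD over baseline SD, the ratio before covariate cost is (1 + c² − 2rc)/[c²(1 − r²)]. At r = 0.7:
- c = 1.25: 0.8125/0.7969 = 1.02
- c = 0.8: 0.52/0.3264 = 1.59

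At c = 1.25 and N = 100 the width ratio is √(1.02/1.032) × 0.987 = 0.98, so in that corner ANCOVA gains nothing.

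**5. Strata.** If strata balanced within arm explain a share s of the variance of change, the z-test SE is too large by 1/√(1 − s): 1.054 at s = 0.1 and 1.118 at s = 0.2. A simulation (400,000 replicates, one balanced binary stratum) gave SE ratios of 1.05 and 1.11 to 1.12, with test size at nominal 5% of about 4% and 3%. Working the other way, the 1.96 cut-off with estimated variances gives 5.3% at 50 per arm and 5.6% at 25 per arm if strata explain nothing. The net direction is unknown.

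**6. Missing week-24 values.** A simulation under no treatment effect (50 per arm, 20–25% dropout, equal correlation between visits) showed no bias in either approach. A likelihood analysis using all visits to week 24 had about 0.65, 0.73 and 0.83 of the z-test's variance at r = 0.3, 0.5 and 0.7. Complete-data baseline adjustment alone gives (1 + r)/2 = 0.65, 0.75 and 0.85, so in that setting most of the gain comes from baseline.

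**The case against.** The strongest reply is that this is a declared simplification in a trial stopped for futility. The deletion of the MMRM is logged with a reason, the redacted SAP 6.6 may say more, and SAP 3.5 removes formal comparisons. On this view the choice of model is an efficiency preference, and one sentence calling the LSS comparison unadjusted and descriptive would settle it. The size of any gain also rests wholly on assumed correlations, variances and stratum effects, and strata may be less balanced than assumed, because SAP 3.3 uses clinical-database values where they differ from the randomisation system.

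Most of this stands as a limit on the size of the point. A reader might infer an undisclosed departure; the revision log rules that out. A reader might infer that LSS data at other visits are discarded; the line plot keeps them in the report, and only the test leaves them out. A reader might infer bias or a compromised confirmatory claim; under randomisation the complete-data comparison is unbiased, bias from missing values is not shown, and no formal testing remains.

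The reply does not remove the conflict between SAP 3.3 and 6.4.2. Nor does the logged reason favour an unadjusted single-visit test, given that the other efficacy tests kept their strata.

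**Conclusion.** The point holds as a matter of consistency and precision, at the level of something to consider. SAP 6.4.2 contradicts SAP 3.3, and it departs openly from protocol 8.5.2.

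Under equal variances, the unadjusted interval is about 5% to 21% wider at 50 per arm and 2% to 17% wider at 25 per arm, for r from 0.7 down to 0.3. The gain would be larger if the week-24 SD is below baseline, and could be nil if it is above. If balanced strata explain 10–20% of the variance of change, the z-test SE is about 5–12% too large. All these inputs are assumptions; the documents supply none of them. No confirmatory conclusion changes.

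**What to change.** Replace the z-test with ANCOVA of week-24 LSS change on baseline score, the two stratification factors and treatment, with a t reference. Alternatively, reinstate the MMRM exactly as protocol 8.5.2 writes it, over all post-baseline visits, and take its week-24 contrast; a version cut at week 24 would be a further departure from the protocol. For each of the four scores, report the adjusted treatment difference with a 95% CI and label any p-value nominal.

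Reconcile SAP 3.3, 3.5 and 6.4.2 so that they agree on whether strata apply to LSS and on the status of the named test. The baseline scores, strata and visit data are already collected, so the cost is programming and a short clarification in the SAP or clinical study report.
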